4.3 Subject withdrawal, replacement and study discontinuation

4.3.1 Subject withdrawal

Subjects **must** be withdrawn from the study at their own request or at the request of their legally acceptable representative. The subject has the right to withdraw from the study at any time for any reason, without the need to justify his/her withdrawal. The subject will not suffer any disadvantage because of the withdrawal.

Subjects **must** also be withdrawn from the treatment period if the β -human chorionic gonadotropin (β -HCG) pregnancy test indicates that they are pregnant at any time between the consent and the EoT Visit.

The subject **may** be withdrawn from the treatment period at the discretion of the investigator due to:

- safety concerns
- lack of clinical benefit (disease progression is not documented but the investigator determines that the subject requires alternative anticancer treatment)
- non-compliance with study procedures to the extent that precludes the assessment of study objectives

Discontinuation of the study drug(s) for documented disease progression is considered study completion and not as premature withdrawal from the study.

All subjects who permanently discontinue study treatment for any reason should have an EoT Visit performed and an STFU phone call as described in the Schedule of Assessments before discontinuation.

The reason for any discontinuation from the study will be documented in the subject's medical record and recorded on the appropriate case report form (CRF).

4.3.2 Subject replacement

In both parts of the study, the sponsor will determine if a subject should be replaced. All subject data collected will be analyzed in the Safety Analysis set. The additional subject(s) included to replace non-evaluable subjects will be given new unique subject IDs.

Part 1 (MT-3724 Dose Escalation)

Subjects who discontinue in cycle 1 and are not evaluable for dose decisions ([Section 3.6.1](#)) must be replaced in the current dose cohort to ensure that a sufficient number of subjects are available for dose decisions. Non-evaluable subjects may remain on treatment if supported by the investigator's assessment of the benefit-risk ratio after consultation with medical monitor.

Subjects who discontinue for any reason after cycle 1 will not be replaced.

Part 2 (MTD Expansion Cohort)

Subjects in Part 2 of the study who have insufficient safety, PD, PK or immunogenicity data in cycle 1 may be replaced at the sponsor's discretion, unless they experienced a TEAE leading to treatment modification.

4.3.3 Study discontinuation

The sponsor has the right to discontinue the study for any reason.

5 TREATMENTS

As a standard precaution for all study drugs, subjects must be treated and observed in an area with equipment/personnel for resuscitation and emergency treatments or have access to emergency facilities through an emergency call. Adequate management and treatment of infusion-related reaction, anaphylactic reaction or other hypersensitivity events according to institutional guidelines must always be assured during the treatment period.

5.1 MT-3724

MT-3724 is the investigational medicinal product (IMP) in this study.

MT-3724 is a recombinant fusion protein consisting of an scFv with affinity for human CD20 cell surface protein, fused to the enzymatically active A1 subunit of Shiga-like Toxin 1.

5.1.1 MT-3724 drug product

MT-3724 will be supplied as a sterile aqueous solution (pH 5.5) in a 2 ml vial containing 2.0ml of MT-3724 (0.5mg/ml) in a formulation buffer comprised of Sorbitol (200mM), Sodium Citrate (20mM) and Polysorbate-20 (0.1%). Vials are shipped frozen. Each vial will be labeled with the drug name, lot number, storage conditions, and US FDA-required Investigational Product statement.

MT-3724 vials must be stored in a secure facility at -20 (-10 to -25) °C until thawed for use. It is recommended to use the thawed drug to prepare the final solution for infusion within 3 hours, although MT-3724 is stable at room temperature for up to 24 hours.

During preparation of the final solution for infusion, MT-3724 is diluted in 5% dextrose in water or normal saline for IV administration. All doses should be administered over 1 hour through an IV line (54 – 75 minutes). See Pharmacy Manual for detailed instructions and worksheets regarding study drug preparation and administration.

Investigational medicinal product must be received at the study site by a designated person, handled and stored safely and properly, and kept in a secured location to which only the investigator and designated staff have access. Upon receipt, the IMP should be stored according to the instructions specified on the label and in the Pharmacy Manual. Clinical supplies are to be dispensed only in accordance with the protocol. Storage conditions must be adequately monitored, and appropriate temperature logs maintained as Source data.

The investigator is responsible for the accountability of the IMP. Records of the receipt and disposition of IMP must be maintained in the trial master file at the site. Records and drug supplies must be available for inspection by the study monitor.

5.1.2 MT-3724 dose selection

The dose of MT-3724 will be calculated based on the subject's body weight (in kilograms [kg]). For MT-3724 dose calculation, the body weight will be measured before the first dose of MT-3724 in cycle 1 (baseline for all subsequent assessments). If the body weight has changed by >10% from the baseline value, this will require re-calculation of the MT-3724 dose or, according to institutional policies should they require adjustment for any change in body weight.

The total administered dose of MT-3724 will be capped at 6000 µg per infusion in all subjects in both parts of the study.

The guidance for treatment modification (dose interruption/delay, dose reduction or treatment discontinuation) is presented in [Section 5.4](#).

Part 1 (MT-3724 dose escalation)

The planned starting dose of MT-3724 in Part 1 will depend on the cohort. Please see [Table 5](#) for doses.

If MT-3724 is not tolerated by any subject in any planned cohort, then additional MT-3724 doses may be evaluated in the interim cohort at the sponsor's discretion in consultation with the investigator(s).

The actual MT-3724 doses in the interim cohorts will be recommended by the sponsor after consultation with the investigator(s). The actual MT-3724 dose in the interim Cohort -1 should not be <5µg/kg/dose, as this was the lowest dose evaluated in the clinic so far.

Part 2 (MTD Expansion Cohort)

The starting dose of MT-3724 in Part 2 will be the MTD of MT-3724 from Part 1.

5.1.3 MT-3724 dosing schedule

MT-3724 will be administered as an IV infusion over 1 hour (window of 54-75 minutes).

Cohort 1-3

For subjects enrolled in Cohorts 1-3, in cycles 1 and 2, MT-3724 infusion should be administered on Day 1, 3, 5, 8, 10 and 12 (± 1) of each 28-day cycle.

Cohorts ≥ 4

In subsequent cohorts in cycles 1 and 2, MT-3724 infusion should be administered on Days 1, 5, 8 and 12 (± 1) of each 28-day cycle. Different dosing days up to D21 may be selected at investigator's discretion after consultation with the medical monitor.

All Cohorts

Starting with cycle 3, MT-3724 will be administered weekly (Day 1, 8, 15 and 22) of each 28-day cycle. Different dosing days within ± 2 days from Day 1, 8, 15 and 22 may be selected at investigator's discretion.

Time windows for days of MT-3724 dosing

Cycles 1-2

Any of the scheduled MT-3724 doses may be administered on different dosing days at investigator's discretion up to D21.

MT-3724 doses must be administered at least 48 hours apart.

Cycles 3 and beyond

Any of the scheduled weekly MT-3724 doses may be administered within ± 2 days at investigator's discretion.

For all cycles

No more than 14 days should elapse between cycles. If more than 14 days elapse, the investigator must consult with the medical monitor before initiating the next cycle of treatment.

5.1.4 Premedication before MT-3724 infusion

One premedication agent from each of the following 3 therapeutic classes must be given within 60 minutes before the start of each MT-3724 infusion in cycle 1 in both parts of the study:

- Oral anti-pyretic agent (325 – 1000mg acetaminophen or equivalent)
- Intravenous H1 histamine receptor antagonist (50 – 100mg diphenhydramine or equivalent)
- Intravenous corticosteroid agent with a shorter biological half-life (125 – 1000mg methylprednisolone or equivalent)

The specific drugs in each class should be selected at investigator's discretion or according to the institutional guideline. Cases where a subject has a contraindicating medical condition that precludes pretreatment with any of the categories above should be discussed with the sponsor. Although continued pre-medication is recommended during all cycles, after cycle 1, the investigator may adjust the dosage and/or avoid using certain premedication agents during the treatment, if supported by the investigator's assessment of the risk from infusion-related reaction, anaphylaxis or other hypersensitivity events.

5.2 Lenalidomide (Revlimid®, LEN)

LEN is an analogue of thalidomide with immunomodulatory, antiangiogenic and antineoplastic activity in cancer.

LEN is available as 2.5-20mg oral capsules. It is available only through a restricted REMS program ([REVLIMID REMS®](#)).

This medicinal product does not require any special storage conditions.

See [Section 5.4.2](#) for guidance about the LEN treatment modification. In addition, the modification of LEN treatment in this study should be guided by the reference prescribing information, as interpreted by the investigator.

5.2.1 Lenalidomide dose selection

The starting dose of LEN in each cohort in Part 1 and Part 2 will be 20mg qd. The LEN starting dose can be decreased per investigator's discretion based on the known safety profile of LEN and subject's status. For Parts 1 and 2, starting with cycle 2 (after completion of the DLT assessment period for Part 1), the investigator may increase the LEN dose to 25mg qd, if clinically indicated, with sponsor approval.

5.2.2 Lenalidomide dosing schedule

In both parts of the current study, subjects will self-administer LEN qd PO with or without food on the first 21 consecutive days (D1-D21) of each 28-day cycle. Subjects will be

directed to self-administer LEN at about the same time every day and record doses taken in subject diary.

Treatment with LEN in the current study will continue until death, disease progression, unacceptable toxicity, withdrawal of consent or another reason for withdrawal, see [Section 4.3](#). If pregnancy occurs during treatment, immediately discontinue the drug.

LEN dosing may be discontinued at investigator's discretion, after approval by the medical monitor. Treatment with MT-3724 as a monotherapy may be permitted to continue with sponsor's approval.

5.3 Intra-subject dose escalation

Intra-subject escalation of MT-3724 dose is not allowed in either part of the study.

If the LEN dose has been reduced due to a TEAE, the intra-subject escalation of LEN dose is permitted if continued treatment is supported by the investigator's assessment of the benefit-risk ratio after consultation with the medical monitor. In such cases, LEN dose may be increased only up to the level before the most recent dose reduction. Starting with cycle 2 (after the DLT assessment period for subjects in Part 1), the dose of LEN may be increased to 25mg qd, as described in [Section 5.2.1](#).

5.4 Treatment modification

Treatment modification due to a TEAE (dose interruption/delay, dose reduction, or permanent discontinuation) could be done in an individual subject at the investigator's discretion after consultation with the medical monitor. By convention in this study, the term 'dose interruption' will be used for the interventions during the IV infusion, and the term 'dose delay' will be used for the changes in the dosing schedule (e.g., date of the next dose) for both MT-3724 and LEN.

The severity of TEAEs requiring treatment modification will be graded according to the CTCAE v.5.0.

5.4.1 MT-3724 treatment modification

Any of the following TEAEs in any treatment cycle may trigger MT-3724 treatment modification, if deemed at least possibly related to MT-3724 by the investigator after consultation with the medical monitor.

- Any TEAE irrespective of the time of onset, that would otherwise fulfill the DLT criteria ([Appendix 4](#))
- Grade ≥ 2 IRR, or another Grade ≥ 2 hypersensitivity reaction
- Any other toxicity related to MT-3724, irrespective of the type or severity or time of onset, that warrants dose modification in the opinion of the investigator after consultation with the medical monitor. This may be Grade 1 or Grade 2 toxicity that notably limits the

activities of daily life (e.g. long-lasting fatigue or anorexia), making a dose reduction necessary to ensure the subject's compliance.

The following actions are recommended after any of the above TEAEs occur.

- The investigator should notify the medical monitor about the TEAE within 24 hours of the awareness.
- The investigator should monitor the subject and if necessary, perform diagnostic procedures and therapeutic interventions.
- If a subject experiences a TEAE in cycle 1 that is related to MT-3724 and qualifies as a DLT, then the MT-3724 treatment should be discontinued, except if continued treatment is supported by the investigator's assessment of the benefit-risk ratio. In this case, the MT-3724 re-treatment should be delayed until the TEAE resolves to Grade ≤ 1 . Further, the MT-3724 re-treatment should start at a $\geq 25\%$ reduced MT-3724 dose.
- If a subject experienced a Grade ≥ 2 IRR, or another Grade ≥ 2 hypersensitivity event, Grade ≥ 2 CRS or Grade ≥ 2 CLS, the investigator should obtain serum samples for cytokines, complement and histamine as soon as possible after the TEAE onset. These samples should be marked "STAT" and shipped immediately to the laboratory.
- MT-3724 dose may be **reduced** by $\geq 25\%$ at the investigator's discretion after consultation with the medical monitor. The number of dose reductions per subject is not limited, except that the reduced dose cannot be $< 5 \mu\text{g}/\text{kg}/\text{dose}$ (this was the lowest dose tested in the clinic so far).
- No intra-subject escalation of MT-3724 dose is permitted after previous MT-3724 dose reduction.

MT-3724 treatment should be **permanently discontinued** if a TEAE that previously led to dose interruption/delay or reduction didn't resolve to Grade ≤ 1 within 4 weeks after treatment modification, except if continued treatment is supported by the investigator's assessment of the benefit-risk ratio after consultation with the medical monitor.

5.4.2 Lenalidomide treatment modification

Any of the following TEAEs in any treatment cycle **may** trigger LEN treatment modification, if deemed at least possibly related to LEN by the investigator.

- Any TEAE that would fulfill the DLT criteria irrespective of the time of onset
- Grade ≥ 2 venous or arterial thrombosis or thromboembolic event
 - LEN treatment should be temporarily discontinued immediately after the onset of the thrombosis or thromboembolic event to assess the causality and clinical risk
 - If the thrombosis is confirmed as at least possibly related to LEN, the LEN treatment may be continued at the investigator's discretion after consultation with the medical monitor after the thrombosis resolves to Grade ≤ 1 . If the treatment is continued, the LEN dose may remain the same dose or be reduced by $\geq 5 \text{ mg qd}$ at the investigator's discretion.

- If the thromboembolic event re-occurs after the LEN continuation and is confirmed as at least possibly related to LEN, then the treatment should be permanently discontinued,
- Grade ≥ 2 skin reactions: skin rash (acneiform or maculo-papular); angioedema or other types of hypersensitivity manifest on the skin, Stevens-Johnson Syndrome, toxic epidermal necrolysis; any other skin reaction that warrants treatment modification at the investigator's discretion
 - LEN treatment should be temporarily discontinued immediately after the onset of the skin reactions to assess the causality and clinical risk
 - If the skin reaction is confirmed as at least possibly related to LEN
 - If Grade 2 (except for Grade 2 non-blistering rash), hold LEN until toxicity resolves to Grade ≤ 1 and reduce LEN dose by ≥ 5 mg qd.
 - If Grade 2 non-blistering rash, hold until toxicity resolves to \leq Grade 1 and continue at same LEN dose or reduce LEN dose by ≥ 5 mg qd
 - If Grade > 3 , the LEN treatment should be permanently discontinued

In addition, the modification of LEN treatment in this study will be guided by the reference prescribing information (REVLIMID[®]), as interpreted by the investigator after consultation with the medical monitor.

5.4.3 Treatment modification due to IRR or other hypersensitivity event

This guidance is applicable to any among the 2 study drugs that, in the investigator's opinion, is at least possibly related to IRR or other hypersensitivity event.

If a subject experienced a Grade ≥ 2 IRR or other Grade ≥ 2 hypersensitivity reaction, the infusion must be immediately interrupted. The following additional actions are recommended in case of a Grade ≥ 2 IRR:

- In case of a Grade 2 IRR or other Grade 2 hypersensitivity reaction
 - Continued treatment with the study drug causally related to IRR may be allowed at the investigator's discretion.
 - If continued treatment is indicated, then
 - it must occur after the appropriate delay (i.e., resolution of symptoms)
 - Upon restarting infusion (and for subsequent doses), if study drug is causally related to IRR, the infusion rate must be reduced by 50% (2-hour duration) preceded by appropriate anti-allergic prophylaxis (see premedication, [Section 5.1.4](#) or the institutional guideline)
- In case of a CTCAE Grade ≥ 3 IRR or other Grade ≥ 3 hypersensitivity reaction, the study drug causally related to IRR should be permanently discontinued.

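### Protocol 5.4.1 can be read to allow reduced-dose MT-3724 re-treatment after a Grade ≥3 infusion or hypersensitivity reaction, where 5.4.3 recommends permanent discontinuation; no precedence is stated

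*Protocol*

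**What the plan says.** **Protocol 5.4.3 (IRR and other hypersensitivity).** The section covers whichever study drug is considered at least possibly related. Its action list opens with "The following additional actions are recommended in case of a Grade" ≥2 IRR.

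- After a Grade 2 reaction, treatment may continue at the investigator's discretion. On restarting, and for later doses, "the infusion rate must be reduced by 50% (2-hour duration) preceded by appropriate anti-allergic prophylaxis".
- After a Grade ≥3 reaction, "the study drug causally related to IRR should be permanently discontinued". No exception follows.

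**Protocol 5.4.1 (MT-3724 treatment modification).** Its triggers apply in any cycle. They include any event that would meet the DLT criteria and any Grade ≥2 "IRR, or another Grade" ≥2 hypersensitivity reaction. The action list begins "The following actions are recommended after any of the above TEAEs occur". Two of its items matter here.

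- Cycle 1 DLT: the item opens "If a subject experiences a TEAE in cycle 1 that is related to MT-3724 and qualifies as a DLT". For that case it recommends stopping MT-3724 unless the investigator's weighing of benefit and risk favours continuing. Re-treatment then waits for recovery to Grade ≤1 and restarts at a dose at least 25% lower.
- Dose reduction: in any cycle, the dose may be cut by at least 25% at the investigator's discretion after consulting the medical monitor.

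**Related text.** Appendix 4 lists a Grade ≥3 IRR or hypersensitivity reaction among the events that may be a DLT. Protocol 3.6.2 places the DLT window in cycle 1 of Part 1. Protocol 5.4 leaves modification in an individual subject to the investigator after consultation with the medical monitor. SAP 3.2 refers back to the protocol for treatment modification.

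**The concern.** One event falls under two sections that end differently. A Grade ≥3 IRR or hypersensitivity reaction attributed to MT-3724 in cycle 1 of Part 1 can be a DLT, and it is also a named trigger of 5.4.1. An investigator working from 5.4.1 finds an exception that allows re-exposure. One working from 5.4.3 finds permanent discontinuation. After cycle 1, or in Part 2, the DLT exception no longer applies, but the general dose-reduction option in 5.4.1 leaves the same question open.

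What is at stake is the safety of the individual subject: re-exposure to a drug that has just caused a severe infusion or hypersensitivity reaction. Section 5.4.1 also states no infusion rate. Read literally, re-treatment after the more severe reaction could run over the standard hour, while 5.4.3 requires a two-hour infusion after the milder one.

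**Working it through.** **Step 1. The two sections side by side, for a Grade ≥3 IRR or hypersensitivity reaction attributed to MT-3724**

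| Feature | 5.4.1 | 5.4.3 |
|---|---|---|
| Covers this event? | Yes, by two triggers (DLT-type event; Grade ≥2 IRR or hypersensitivity) | Yes, by its title and its Grade ≥3 item |
| Default for a cycle 1 DLT | Discontinue | Discontinue permanently |
| Exception | Investigator's benefit-risk assessment | None written |
| Conditions on re-treatment | Recovery to Grade ≤1; dose cut ≥25% | Not applicable |
| Other route to continued dosing | Dose cut ≥25% in any cycle, after medical-monitor consultation | None written |
| Infusion rate on re-treatment | Not stated | Halved, but only under the Grade 2 item |
| Force | Recommended | Recommended |
| Statement of precedence | None | None |

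The sections part only when an investigator uses the 5.4.1 exception or its dose-reduction option.

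**Step 2. Hourly delivery, as an illustration**

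Inputs:
- standard infusion time T = 1 hour (Protocol 5.1.3);
- minimum dose cut 25% (5.4.1);
- rate cut 50% after Grade 2 (5.4.3).

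Let D be the original dose.

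- Original infusion: D / 1 h = 1.00 D per hour.
- Check on the plan's own figure: D at half the rate takes D / (0.50 D per hour) = 2 hours, which agrees with 5.4.3.
- 5.4.1 path at the minimum cut over the standard hour: 0.75 D / 1 h = 0.75 D per hour.
- 5.4.3 path after Grade 2 at full dose: D / 2 h = 0.50 D per hour.
- Ratio: 0.75 / 0.50 = 1.5.

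The permitted infusion window of 54 to 75 minutes does not alter this. If a subject's usual infusion time is T, the ratio is (0.75 D / T) / (0.50 D / T) = 1.5 for any T.

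At the planned dose levels in Protocol Table 5, over one hour and ignoring the 6000 µg cap:

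| Dose (µg/kg) | 5.4.1 path, 0.75 × dose (µg/kg/h) | 5.4.3 after Grade 2, 0.50 × dose (µg/kg/h) |
|---|---|---|
| 10 | 7.5 | 5 |
| 20 | 15 | 10 |
| 25 | 18.75 | 12.5 |
| 50 | 37.5 | 25 |

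To match the Grade 2 rate over one hour, the cut x must satisfy 1 − x = 0.50, so x = 50%. The total dose per infusion runs the other way: 0.75 D on the 5.4.1 path against 1.00 D on the Grade 2 path.

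**Step 3. Effect on the trial's results**

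A DLT is counted when the event occurs. Under Protocol 3.6.1 a subject with a DLT after at least one MT-3724 dose in cycle 1 is evaluable for dose decisions, whatever happens afterwards. The DLT count and the MTD rule in 3.6.3 therefore do not depend on which section is followed. SAP 8.2.6 and 8.2.7 tabulate events and the actions they led to, and no definition there changes.

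**The case against.** **The event-specific section governs.** Section 5.4.3 is written for exactly this event, and its Grade ≥3 item has no exception, whereas 5.4.1 spells its exceptions out. Section 5.4.5 shows the same layering: AST or ALT above 8 × ULN can be a DLT and so falls under the 5.4.1 exception, yet Table 7 calls for permanent discontinuation. This is the natural reading, and it limits the weight of the point. It remains an inference. Section 5.4.1 names IRR and hypersensitivity among its own triggers without excluding the severe grades, and nothing tells the reader to prefer 5.4.3.

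**Both sections default to stopping and only recommend.** This stands. A reader might infer that the protocol directs re-exposure after a severe reaction, or that it contains two contradictory mandates. It does neither: 5.4.1 opens an exception to a default of discontinuation, and 5.4 calls for medical-monitor consultation.

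**The infusion-rate gap rests on silence.** This also stands in part. Section 5.4.1 sets no rate for any event, and its silence does not cancel the slow-infusion rule after Grade 2. An investigator who re-treated might well slow the infusion anyway. That is why the rate is a secondary point.

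**Other safeguards exist.** Section 5 requires that management of infusion and hypersensitivity reactions be assured throughout treatment, and 5.4.1 recommends telling the medical monitor within 24 hours. A reader might infer that re-treatment could proceed without prophylaxis. In cycle 1 it could not, because 5.1.4 makes premedication from three classes mandatory before every infusion. From cycle 2 premedication is recommended, but the investigator may adjust it or omit agents. None of this decides whether re-treatment is allowed.

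**Conclusion.** The inconsistency is in the text and should be removed. For a Grade ≥3 infusion or hypersensitivity reaction attributed to MT-3724, 5.4.1 can be read to allow reduced-dose re-treatment that 5.4.3 recommends against without exception, and the protocol does not say which prevails.

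Its weight is modest. The circumstances are narrow, and few cases seem likely, but that is an assumption. The documents give no IRR rate, and the monotherapy DLTs described in Protocol 1.6 are cytokine release and capillary leak events.

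Two stronger inferences are not supported:

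- **The ratio of 1.5 as a risk multiple.** It assumes the minimum 25% cut and an unchanged infusion time. Nothing in the documents makes hourly delivery the measure of re-challenge risk. The 5.4.1 path also carries conditions absent from the Grade 2 path: recovery to Grade ≤1 and a lower dose.
- **An effect on dose-finding or analysis.** There is none on DLT counts, the MTD or the analyses, for the reasons in Step 3 of the check.

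**What to change.** Add one clause to Protocol 5.4.1, for example: *The cycle 1 re-treatment exception and the dose-reduction option in this section do not apply to Grade ≥3 IRR or other Grade ≥3 hypersensitivity reactions attributed to MT-3724, which are governed by Section 5.4.3.*

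The drafting cost is a single clause, with no change to the DLT rules, sample size or analyses. The real cost is clinical: the investigator loses the discretion to re-challenge in these cases. If the sponsor wants to keep that discretion, the exception belongs in 5.4.3, with an infusion rate no faster than the one required after Grade 2 and mandatory premedication for all later doses. That trade-off is a clinical decision for the sponsor.
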